#### 6.2 Component 1: Identify FT596 MTD When Given on Day 30 Only

In Component 1, all patients will receive a single dose of FT596 on Day 30 (+3 days) post-transplant. Rituximab (Rituxan or an FDA approved biosimilar, e.g. Truxima and Ruxience) 375 mg/m^2 is administered 2-3 days prior to FT596.

Up to three FT596 dose levels are planned: Dose Level 1:  $9x10^7$  cells/dose, Dose Level 2:  $3x10^8$  cells/dose, Dose Level 3:  $9x10^8$  cells/dose with a Dose Level -1:  $3x10^7$  cells/dose tested only if DLT at DL1. Refer to Section 3 regarding the required staggering of enrollment.

#### Dose limiting toxicity for Component 1 is defined as:

Component 1 dose limiting toxicity is defined as any of the following events within 28 days after the FT596 dosing based on CTCAE v5:

- Grade 4 hematologic toxicity lasting > 7 days (not including lymphopenia)
- Grade 4 non-hematologic toxicity
- Grade ≥3 FT596 Infusion Related Reaction
- Grade 2 acute GVHD that requires steroid therapy >7 days or progression after 3 days of steroids or has partial response after 14 days of treatment
- Grade ≥3 acute GVHD
- Grade 4 cytokine release syndrome (CRS)
- Grade 3 CRS that does not resolve to < Grade 2 in 72 hours
- Grade 3 neurotoxicity
- Grade 3 organ toxicity involving vital organs; cardiac, central nervous system and pulmonary that lasts longer than 7 days including Grade 3 Investigations (laboratory values) of any duration that indicate damage to vital organs.
- Any Grade 3 non-hematological toxicity that does not resolve to ≤Grade 2 within 72 hours; excepting Grade 3 renal and hepatic toxicity which may take up to 7 days to resolve to ≤Grade 2

#### 6.3 Component 2: Safety of FT596 when given at Day 7 based on the MTD from Component 1

Prior to the start of enrollment in Component 2, a summary of patient data from Component 1 will be submitted to the FDA for their review. Included in this report will be enrollment and treatment information, a summary of adverse events, DLT's SR events and SAEs as well as any disease status information. Component 2 may proceed if permission is received from the FDA. Otherwise the study will stop. In Component 2, all patients will receive a single dose of FT596 on Day 7 (+3 days) post-transplant. Rituximab (Rituxan or an FDA approved biosimilar, e.g. Truxima and Ruxience) 375 mg/m^2 is administered 2-3 days prior to FT596.

Up to two dose levels of FT596 are planned (one dose level below the MTD from Component 1 and the MTD from Component 1). Any two sequential dose levels of FT596 may be included: Dose Level -1:  $3x10^7$  cells/dose, Dose Level 1:  $9x10^7$  cells/dose, Dose Level 2:  $3x10^8$  cells/dose, Dose Level 3:  $9x10^8$  cells/dose. Refer to Section 3 regarding the required staggering of enrollment.

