#### **12 Statistical Considerations**

#### 12.1 Study Designs

This study consists of two components. The 1st component is a Phase I clinical trial to identify the maximum tolerated dose (MTD) of FT596 at Day 30 post FT596 infusion. The second component is a Phase I clinical trial to identify the MTD of FT596 at Day 7 post FT596 infusion. Rituximab is given 2-3 days before FT596. In addition to identifying the MTD and providing preliminary estimates of safety, secondary objectives include providing preliminary descriptive estimates of efficacy such as progression-free survival, relapse and non-relapse mortality along with their error measurements. Correlative objectives include measurement of the persistence of FT596 in blood after each FT596 infusion by immunophenotyping and PCR up to 1 year, the association of FT596 persistence with safety and anti-tumor activity.

Component 1 will identify the MTD of FT596 when given as a single dose at Day 30. Up to three FT596 dose levels are planned (Dose Level 1:  $9x10^7$  cells/dose, Dose Level 2:  $3x10^8$  cells/dose, Dose Level 3:  $9x10^8$  cells/dose with a Dose Level - 1:  $3x10^7$  cells/dose tested only if DLT at DL1).

**Component 1 dose limiting toxicity** is defined as any of the following events within 28 days after the FT596 dosing based on CTCAE v5:

- Grade 4 hematologic toxicity lasting > 7 days (not including lymphopenia)
- Grade 4 non-hematologic toxicity
- Grade ≥3 FT596 Infusion Related Reaction
- Grade 2 acute GVHD that requires steroid therapy >7 days or progression after 3 days of steroids or has partial response after 14 days of treatment
- Grade ≥3 acute GVHD
- Grade 4 cytokine release syndrome (CRS)
- Grade 3 CRS that does not resolve to < Grade 2 in 72 hours
- Grade 3 neurotoxicity

- Grade 3 organ toxicity involving vital organs; cardiac, central nervous system and pulmonary that lasts for longer than 7 days including Grade 3 Investigations (laboratory values) of any duration that indicate damage to vital organs.
- Any Grade 3 non-hematological toxicity that does not resolve to ≤Grade 2 within 72 hours; excepting Grade 3 renal and hepatic toxicity which may take up to 7 days to resolve to ≤Grade 2

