#### 12.4.4 Any Two Grade 4 Dose Limiting Toxicities (DLTs)

If two Grade 4 DLTs occur, enrollment will be halted and reviewed by the study team with follow-up notification to the FDA and IRB of the findings before enrollment is restarted.

#### 12.4.5 Grade 4 Lymphopenia (<200 cells/uL) at Day 100

The goal is to construct a boundary based on lymphopenia such that the probability of early stopping is at most 10% if the rate is equal to 20% and our sample size is at most 18. With these stipulations, the trial will be stopped and reviewed if 3/4, 4/7, 5/10, 6/13 or 7/17 patients at any time have Grade 4 related lymphopenia at Day 100.

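### The DLT lists name Grade 4 toxicity without Grade 5, and the plan does not say how a fatal toxicity is scored in the CRM

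*Combined protocol and SAP*

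**What the plan says.** A DLT is "any of the following events within 28 days after the FT596 dosing based on CTCAE v5" (Section 6.2; Section 12.1 matches). The list mixes three kinds of item.

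- Open upward: "Grade ≥3 FT596 Infusion Related Reaction" and "Grade ≥3 acute GVHD".
- A single grade: "Grade 4 non-hematologic toxicity", Grade 4 CRS and "Grade 3 neurotoxicity".
- A grade with a time condition: Grade 4 hematologic toxicity that must persist beyond 7 days, Grade 3 vital-organ toxicity beyond 7 days (laboratory findings of any duration), and "Any Grade 3 non-hematological toxicity that does not resolve to ≤Grade 2 within 72 hours".

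The bare Grade 4 wording appears in every copy of the list: synopsis, schema, 6.2, 6.3 and 12.1. No copy names Grade 5 or death.

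Grade 5 is used elsewhere. The adverse event table in 10.2 has a column for Grades 4 and 5 together, and 10.5 records death from disease as a Grade 5 neoplasm. Section 6.1.2 lists death beside dose limiting toxicity as a separate thing to monitor.

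Death after FT596 up to Day 100 post-transplant is a stopping event (6.4). Section 12.4.1 then halts enrollment for study team review, with FDA and IRB notification before restart. For DLTs, 12.4.4 says "If two Grade 4 DLTs occur, enrollment will be halted".

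**The concern.** The DLT count is the only patient outcome that enters the CRM, and the CRM determines the MTD, which is the primary objective. The authors wrote the upward sign for two items and omitted it for others, so a literal reader can take the omission as deliberate. On that reading the worst outcome of a toxicity can score lower than a survivable Grade 4 event of the same kind.

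The cohorts have three patients and the prior toxicity rates are very low. The scoring of one patient can therefore decide whether the next cohort moves up a dose level. The review after a death protects patients during the halt, but it does not settle whether that patient counts as 0 or 1 once enrollment restarts.

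**Working it through.** **Step 1: which fatal events can fall outside the list.** This compares the list with the plan's own grading scales.

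- Infusion reaction and acute GVHD: covered at any grade from 3 up.
- CRS: Section 10 takes it out of CTCAE and grades it on the ASTCT table, printed with Grades 1 to 4. A fatal case would be at most Grade 4 there, and Grade 4 CRS is listed.
- Neurotoxicity: Section 7.4 uses the ASTCT ICANS table, also printed with Grades 1 to 4. Grade 4 falls under the Grade 4 non-hematologic item.
- Other non-hematologic toxicity (infection, cardiac, pulmonary): graded on CTCAE. If recorded only as Grade 5, it meets no item as written.
- Items requiring more than 7 days: a patient who dies sooner cannot meet them. For the 72-hour item the text does not say whether death before 72 hours counts as failure to resolve.

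**Step 2: what the choice of score does.** The plan gives no figure for this, so there is none to reproduce. Inputs are from Section 12.1:

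- power model, P_i = p_i^exp(α)
- α normal with mean 0 and variance 2
- skeleton 1%, 3%, 6% for Component 1, and 5%, 10% as the example for Component 2
- target ≤25%, cohorts of 3, no escalation of more than one level

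The likelihood is the product over doses of P_i^y_i × (1 − P_i)^(n_i − y_i). The posterior mean of α (written a) comes from numerical integration, and the dose estimate is p_i^exp(a).

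Component 1, first cohort of 3 at Dose Level 1 with one fatal toxicity:

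- Scored 0/3: a = 0.522, exp(a) = 1.686, and 0.01^1.686 = 0.04%. The three doses are 0.04%, 0.27%, 0.87%. The CRM escalates to Dose Level 2.
- Scored 1/3: a = −1.262, exp(a) = 0.283, and 0.01^0.283 = 27.2%. The three doses are 27.2%, 37.1%, 45.1%. The CRM does not escalate.

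If the probabilities are averaged over the posterior instead, the values are 4.0%, 6.3%, 8.7% and 28.8%, 37.1%, 44.0%. The decisions are the same.

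Component 2, first cohort at the lower of the two doses:

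- Scored 0/3: a = 0.697, exp(a) = 2.007, and 0.05^2.007 = 0.2%. The doses are 0.2% and 1.0%. The CRM escalates.
- Scored 1/3: a = −0.919, exp(a) = 0.399, and 0.05^0.399 = 30.3%. The doses are 30.3% and 39.9%. The CRM does not escalate.

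**Step 3: later cohorts in Component 1.** Here the effect depends on how the ≤25% target is applied.

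- Dose Level 2 after a clean first cohort: 0/3 escalates to Dose Level 3. 1/3 gives 10.5%, 17.9%, 25.2%, which selects Dose Level 3 if the rule is closest to 25%, and Dose Level 2 if 25% is a strict cap.
- Dose Level 3 after two clean cohorts, one Grade 4 and one fatal event: read as 1/3, the Dose Level 3 estimate is 14.6%. Read as 2/3, the doses are 11.5%, 19.2%, 26.6%. Under the closest rule Dose Level 3 is still chosen (1.6 points from target against 5.8 for Dose Level 2). Only a strict cap changes the dose.

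**The case against.** A reader might infer that any fatal CRS, neurotoxicity, infection or organ toxicity counts as a non-event and that escalation follows. The documents do not support that.

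- **CRS and neurotoxicity.** On the printed tables a fatal case is graded no higher than 4, and Grade 4 is covered for both. This stands. What remains is that the lists are headed CTCAE v5 while Sections 7.4 and 10 send these two to other scales.
- **Events before death.** The list counts qualifying events within 28 days, not final grade. A toxicity documented at Grade 4, or at a qualifying Grade 3, before death already counts. The plan does not say that events are recorded only at maximum grade. This stands, and limits the gap to deaths with no recorded qualifying stage.
- **The mortality rule.** The DLT window lies inside the Day 100 window. Component 1 runs to Day 30 to 33 plus 28, that is Day 58 to 61. Component 2 runs to Day 7 to 10 plus 28, that is Day 35 to 38. Adding a further 7 days for a rituximab-related delay still leaves both before Day 100. With 12.4.1 read as acting on a single death, every death in the DLT window halts enrollment, so no escalation would go unreviewed. Component 2 also needs FDA permission. This stands as a safeguard, but neither 12.4 nor 12.1 says how the death is scored when the CRM resumes.
- **Intent.** The study team would probably count such a death. That is likely, but the primary endpoint should not rest on it.

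**Conclusion.** The wording should be corrected. The lists omit Grade 5 for hematologic and non-hematologic toxicity, and no section says how a fatal toxicity is scored in the CRM. A CTCAE-graded toxic death recorded only as Grade 5 can therefore be read as no DLT, and one that cuts short a duration criterion has no defined score.

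Where this happens in a first cohort, it reverses the dose decision in both components: 0.04% against 27.2% at Dose Level 1, and 0.2% against 30.3% with the Component 2 example skeleton. In later Component 1 cohorts the decision may or may not change, depending on how the ≤25% target is applied.

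These figures assume the stated prior and skeletons, one fatal event in a cohort of three, and no qualifying Grade 3 or 4 stage on record. How often that would occur cannot be judged from the documents. They do not support a claim that toxic deaths in general are missed, or that the trial would escalate after one without review.

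**What to change.** - In every copy of the DLT list (synopsis, schema, 6.2, 6.3, 12.1), write the non-hematologic item so that it includes Grade 5, consistent with the use of that grade in 10.2 and 10.5.
- In 12.1, state how a fatal toxicity within the 28-day window is scored in the CRM, including when death prevents a duration qualifier from being met. Adding the upward sign to the hematologic item alone would not do this, because the 7-day condition would remain.
- Say in the list which scale governs CRS and neurotoxicity.
- In 12.4.1, cross-refer to the scoring statement, so that the mortality review and the CRM input are linked.
- Make the Grade 4 DLT wording in 6.4 and 12.4.4 consistent with the revised list. The two sections also differ on the count: 6.4 lists any such event and 12.4.4 requires two. They must be reconciled. For deaths this is a matter of consistency only, since 12.4.1 already halts enrollment.

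The cost is wording in an amendment. No patients, visits or procedures are added, and the CRM model does not change.

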#### Dose limiting toxicity for Component 2 is defined as:

Component 1 dose limiting toxicity is defined any of the following events within 28 days after the FT596 dosing based on CTCAE v5:

- Grade 4 hematologic toxicity lasting > 7 days (not including lymphopenia)
- Grade 4 non-hematologic toxicity
- Grade ≥3 FT596 Infusion Related Reaction
- Grade 2 acute GVHD that requires steroid therapy >7 days or progression after 3 days of steroids or has partial response after 14 days of treatment
- Grade ≥3 acute GVHD
- Grade 4 cytokine release syndrome (CRS)
- Grade 3 CRS that does not resolve to < Grade 2 in 72 hours
- Grade 3 neurotoxicity
- Grade 3 organ toxicity involving vital organs; cardiac, central nervous system and pulmonary that lasts longer than 7 days including Grade 3 Investigations (laboratory values) of any duration that indicate damage to vital organs.
- Any Grade 3 non-hematological toxicity that does not resolve to ≤Grade 2 within 72 hours; excepting Grade 3 renal and hepatic toxicity which may take up to 7 days to resolve to ≤Grade 2
- Non-engraftment by Day 28 post-transplant

#### 6.4 Monitoring for Excessive Toxicity (Component 1 and Component 2)

Each component will be monitored independently for the following events of excessive toxicity occurring after the FT596 infusion based on Day 0 as the Transplant Day (ONLY POST FT596 EVENTS COUNT HERE) per Section 12.4

- Mortality by Day 100
- Grade III-IV Acute GVHD by Day 100
- Any Grade 4 FT596 Infusion Related Reaction
- Any Grade 4 Dose Limiting Toxicity (DLT) event
- Grade 4 Lymphopenia (<200 cells/uL) at Day 100
- Engraftment failure by Day 28 (Component 2 only)

#### 6.5 Permitted and Prohibited Concomitant Medications/Therapies

Primary supportive care is to continue according to the primary transplant protocol. In order to provide optimal patient care and to account for individual medical conditions, investigator discretion may be used in the prescribing of all supportive care drug therapy (i.e. acetaminophen, diphenhydramine, antimicrobials, etc.).

Because they may inhibit NK cell function, systemic corticosteroids should be avoided during the treatment period (3 days before the first FT596 through 14 days after) unless absolutely required. Intravenous glucocorticoid as premedication for rituximab may be administered per the USPI or institutional guidelines. Methylprednisolone should be used as preferred glucocorticoid premedication given its shorter half-life.

Glucocorticoids should not be used as premedication for FT596.

#### 6.6 Duration of Treatment

Treatment consists of a single dose of rituximab or an FDA approved biosimilar followed 2-3 days later by FT596 at the patient's assigned dose/schedule. If a patient cannot receive FT596 by 7 days after rituximab due to unresolved infusion related toxicity (refer to Section 6.1), FT596 is not given.

All patients receiving at least one dose of FT596 will be followed per Section 8.1.

#### 6.7 Duration of Study Participation

Follow-up for disease and survival endpoints continues through 1 year post-transplant.

Direct study participation ends approximately 30 days after the last FT596 infusion and once an End of Treatment visit has occurred.

Clinical information including disease status and potential late toxicities associated with FT596 will be abstracted from follow-up visits associated with the transplant at Day 100, Day 180, Day 270 (if done), and Day 365. After Day 365 (1 year), the patient's follow-up will transfer to a designated long-term follow-up protocol per Section 6.8.

Rituximab or the FDA approved biosimilar may continue (independent of this study) per institutional practice.

#### 6.8 Continuation of Follow-Up via a Separate Long-Term Follow-Up Protocol

FT596 is an engineered cellular immunotherapy product and the long-term safety risk is not known and may include conditions with delayed onset relative to FT596 administration. Specific conditions potentially related to engineered cellular immunotherapy products such as FT596, including but not limited to, new malignancies, new or worsening neurologic disorders, new or worsening autoimmune or rheumatologic disorder, or new hematologic disorder will be documented and reported to the FDA as part of IND the annual report.

At the end of the follow-up period for this study, follow-up for up to 15 years from the first FT596 cell infusion will continue on a separate long-term follow-up (LTFU) study (UMN CPRC#2020LS052). Consent to the LTFU study is obtained at the time of consent for the treatment study.

#### 7 Management of Potential Toxicities Associated FT596

No FT596 clinical data are available.

The long-term safety risk is not known and may include conditions with delayed onset relative to FT596 administration.

The information provided below is extrapolated from other NK cell products and other cell products in general.

All adverse events will be defined and graded using the Common Terminology Criteria for Adverse Events (CTCAE) Version 5.0 https://ctep.cancer.gov/protocoldevelopment/electronic\_applications/docs/CTCAE\_ v5\_Quick\_Reference\_5x7.pdf

#### 7.1 Infusion Related Reaction Associated with FT596

Patients will be observed for the occurrence of acute allergic/anaphylactoid infusion reactions such as rigors and chills, rash, urticaria, hypotension, dyspnea, and angioedema during and after the infusion.

The management of acute infusion or allergic reactions that occur during FT596 administration is described below.

# If Grade 4 Infusion-Related Reaction (Life-threatening consequences; urgent intervention indicated):

Stop FT596 administration. Do not restart.

The volume of FT596 administered prior to the infusion-related reaction must be documented; retain any remaining product and contact [name] or designee for further instructions.

If Grade ≤3 Infusion-Related Reaction (e.g., not rapidly responsive to symptomatic medication and/or brief interruption of infusion); recurrence of symptoms following initial improvement; hospitalization indicated for clinical sequelae):

- Interrupt FT596 administration.
- Manage symptoms, e.g., with antihistamines, antipyretics and analgesics, according to standard institutional practice standards.
- Resume FT596 administration only upon complete resolution of the infusionrelated reaction and at the discretion of the Investigator. Given that FT596 administration may involve single or multiple bags depending on the total planned dose and accounting for the stability of FT596 post-thaw, FT596 administration may continue following resolution to a Grade 1 infusion-related reactions as follows:

#### If single-bag FT596 dosing:

- No additional FT596 may be administered.
- The volume of FT596 administered prior to the infusion-related reaction must be documented; retain any remaining product and contact the Study PI (or designee) for further instruction.
- Additional bags may not be administered to make up for FT596 that was not administered from the bag during which the infusion-related reaction occurred.

#### If multiple-bag FT596 dosing:

- The volume of FT596 administered from the bag during which the infusionrelated reaction occurred must be documented; retain any remaining product from the bag and contact the Sponsor for further instruction.
- If dosing with additional FT596 bags was planned, they may be thawed and administered.
- Additional bags beyond what was originally planned may not be administered to make up for FT596 that was not administered from the bag during which the infusion-related reaction occurred.

#### 7.2 DMSO Related Risks

FT596 is formulated in DMSO to enable cryopreservation. DMSO side effects and symptoms are generally associated with histamine release and include coughing, flushing, rash, chest tightness and wheezing, nausea and vomiting, and cardiovascular instability. Treat by slowing the rate of infusion, medicating with antihistamines, and treating symptoms per institutional practice. Recommended patients receive IV hydration with normal saline (NS) 250 ml bolus before and 250 ml bolus after FT596 administration to reduce the potential risks associated with DMSO.

#### 7.3 Cytokine Release Syndrome (CRS) or CRS-Like Symptoms

While CRS is a clearly defined syndrome with T-cell therapy, it is generally not believed to be a toxicity associated with NK cell therapies unless administered with cytokines that may independently drive the proliferation and activation of CD8+ T cells, e.g., exogenous IL-15 (Cooley 2019).

If CRS is suspected, CRP and ferritin levels should be assessed locally, and a research related serum sample should be collected for an IL-6 level (if feasible).

CRS must be graded as outlined in the ASTCT CRS consensus grading system per Section 10 (Lee 2019).

If CRS occurs (e.g. a differential diagnosis is recorded in the institutional medical record), CRP and ferritin levels should be done three times weekly until the resolution of CRS per Section 8.1. In addition, a research related serum sample should be collected for an IL-6 level at the time of any change (increase or decrease) in the CRS grade. Because patients may be outpatients any missed collection time points will not be a protocol deviations.

Management of CRS should follow the recommended management algorithm provided in Table 1 (Neelapu 2018) and/or institutional practice.

Table 1: Recommendations for the Management of Cytokine Release Syndrome						
Grade	Sign/Symptom	Management				
Grade 1	Fever or organ toxicity	
 
Acetaminophen and hypothermia blanket for the treatment of fever
 
Ibuprofen can be used as second treatment option for fever, if not contraindicated
 
Assess for infection using blood and urine cultures, and chest radiography
 
Empiric broad-spectrum antibiotics and filgrastim if neutropenic
 
Maintenance IV fluids for hydration
 
Symptomatic management of constitutional symptoms and organ toxicities
 
Consider tocilizumab 8 mg/kg a IV or siltuximab 11 mg/kg IV for persistent (lasting ≥3 days) and refractory fever
 
				
Grade 2	Hypotension	
 
IV fluid bolus of 500–1,000 mL of normal saline
 
Can give a second IV fluid bolus if systolic blood pressure remains <90 mmHg
 
Tocilizumab 8 mg/kg a IV or siltuximab 11 mg/kg IV for the treatment of hypotension that is refractory to fluid boluses; up to 3 additional doses of tocilizumab may be administered, and the interval between consecutive doses should be at least 8 hours.
 
If hypotension persists after two fluid boluses and anti-IL-6 therapy, start vasopressors, consider transfer to ICU, obtain echocardiogram, and initiate other methods of hemodynamic monitoring
 
In subjects at high-risk b or if hypotension persists after 1–2 doses of anti-IL-6 therapy, dexamethasone can be used at 10 mg IV every 6 hours
 
Manage fever and constitutional symptoms as in Grade 1
 
				
	Hypoxia	
 
Supplemental oxygen
 
Tocilizumab or siltuximab ± corticosteroids and supportive care, as recommended for the management of hypotension
 
				
	Organ toxicity	
 
Symptomatic management of organ toxicities, as per standard guidelines
 
Tocilizumab or siltuximab ± corticosteroids and supportive care, as indicated for hypotension
 
				
Grade 3	Hypotension	
 
IV fluid boluses as needed, as recommended for the treatment of Grade 2 CRS
 
Tocilizumab and siltuximab as recommended for Grade 2 CRS, if not administered previously
 
Vasopressors as needed
 
Transfer to ICU, obtain echocardiogram, and perform hemodynamic monitoring as in the management of Grade 2 CRS
 
Dexamethasone 10 mg IV every 6 hours; if refractory, increase to 20 mg IV every 6 hours
 
				

Table 1: R	Table 1: Recommendations for the Management of Cytokine Release Syndrome					
Grade	Sign/Symptom Management					
		
 
Manage fever and constitutional symptoms as indicated for Grade 1 CRS
 
				
	Hypoxia	
 
Supplemental oxygen including high-flow oxygen delivery and non-invasive positive pressure ventilation
 
Tocilizumab or siltuximab plus corticosteroids and supportive care, as described above
 
				
	Organ toxicity	
 
Symptomatic management of organ toxicities as per standard guide
 
Tocilizumab or siltuximab plus corticosteroids and supportive care, a described above
 
				
	Hypotension	
 
IV fluids, anti-IL-6 therapy, vasopressors, and hemodynamic monitoring as defined for the management of Grade 3 CRS
 
Methylprednisolone 1 g/day IV
 
Manage fever and constitutional symptoms as in Grade 1 CRS
 
				
Grade 4	Hypoxia	
 
Mechanical ventilation
 
Tocilizumab or siltuximab plus corticosteroids and supportive care, as described above
 
				
	Organ toxicity	
 
Symptomatic management of organ toxicities as per standard guidelines
 
Tocilizumab or siltuximab plus corticosteroids and supportive care, as described above
 
				

CRS, cytokine release syndrome; ICU, intensive care unit; IV, intravenous.

NOTE: All medication doses indicated are for adults.

a Maximum amount of tocilizumab per dose is 800 mg.

b High-risk subjects include those with bulky disease and those with comorbidities.

Reference: Neelapu 2018., Actemra USPI

